APPENDIX 2 PART 2 SCHEDULE OF STUDY PROCEDURES - MULTIPLE, ASCENDING DOSES

Table 5 Part 2 (MAD): Screening, Dosing Periods, and Follow up – High-Level

		High-level Treatment and Observation												
Day	-28 to -1	1	2	3	4	5	6	7	8	9	10	11	12	16± 1
Period	Screen ^a	Baseline Single-blind Placebo BID		Double-blind Treatment BID								Follow Up		
CONFINED:														
Confinement in the unit ^b with telemetry		Admission	←						→	Discharge				
NON-CONFINED^b:														
Clinic visit mandatory ^c	X	AM, 3PM	AM, 7h	X (all day)	7h			AM		X (all day)	AM	AM	X	X
Clinic visit (optional) or HHN visit ^d		PM	PM		AM, PM	AM, PM	AM, PM	PM	AM, PM					
All Dosing and Assessments below apply to both CONFINED or NON-CONFINED Patients														
Informed consent	X													
Single-blind placebo administration		X Q12h	X Q12h											
Randomized DB IMP administration ^e				X Q12h	X Q12h	X Q12h	X Q12h	X Q12h	X Once (AM)					
Assessment of dose-modification/stopping criteria ^f		←							→					
Medical history	X													
Physical examination ^g	X	X		X				X±1d		X	X	X	X	
Body height	X													
Body weight	X			X							X			
Vital signs ^h	X	X	X	X	X	X	X	X	X	X	X	X	X	

High-level Treatment and Observation																								
Day	-28 to -1	1	2	3	4	5	6	7	8	9	10	11	12	16± 1										
Period	Screen ^a	Baseline Single-blind Placebo BID										Follow Up												
AEs/SAEs ⁱ	↔																							
Prior/concomitant therapy (incl. stable HF background treatment) ^j	↔																							
TTE ^k	X	X 3pm	X 0, 7h	X 0, 7h	X 7h			X 0h		X 0, 7hr	X 24h	X 48h												
ECG telemetry ^l		↔																						
Holter ECG ^m		↔						↔																
12-lead ECGs ⁿ	X		X 0h	X 0, 7h	X 7h			X±1d		X 0h	X 24h	X 48h		X										
ICD download ^o														X (± 1w)										
Serology ^p	X																							
Pregnancy test ^q	X													X										
FSH level ^r	X																							
Hematology ^s	X		X		X 7h			X±1d		X		X		X										
Chemistry ^t	X		X		X 7h			X±1d		X		X		X										
Urinalysis ^s	X									X														
Troponin ^t	X		X 0h	X 0,7h	X 7h			X±1d		X 0h	X 24h	X 48h		X										
NT-proBNP	X		X	X						X				X										

		High-level Treatment and Observation													
Day	-28 to -1	1	2	3	4	5	6	7	8	9	10	11	12	16± 1	
Period	Screen ^a	Double-blind Treatment BID												Follow Up	
PK (plasma) ^w				X Mult	X 0, 7h				X 0h		X Mult	X 24h	X 48h	X 72h	

AE, adverse event; BP, blood pressure; bpm, beats per minute; CK-MB, creatine kinase-MB; DB, double-blind, [REDACTED]; ECG, electrocardiogram; eCRF, electronic case report form; HF, heart failure; HHN, home health nurse; HR, heart rate; ICD, implantable cardioverter defibrillator; ICF, informed consent form; IMP, investigational medicinal product; PK, pharmacokinetic; Pk/Tr, peak/trough; Q12h, every 12 hours; SAE, serious adverse event; SRC, Safety Review Committee; TTE, transthoracic echocardiography.

- ^a Patients with LVEF < 25% may be screened for up to 12 weeks to accommodate SRC review of first 3 patients of each cohort. Patients must remain clinically stable to meet eligibility.
- ^b **If a patient has an ICD, confinement is not required.** The patient may elect to stay in close proximity to the investigational site (eg, at a nearby hotel), but must return to the clinic for all IMP administrations and assessments. Alternatively, patients may be visited by a home health nurse for IMP administrations and assessments not requiring central equipment.. For all patients, ECGs, TTEs, and PK blood draws will be performed at the study site. If a patient is not confined, it is expected that the home health nurse will be in daily contact with the study site. All patients will be discharged from clinical research unit on Day 11 after all procedures have been completed and the investigator deems it safe.
- ^c For Day 3 and Day 9, a clinic visit from morning AM (pre-dose) until evening PM dose (12h later) is required. Refer to [Table 6](#) for a detailed schedule
- ^d Randomization will occur on Day 3 following local labs on Day 2. For patients who are not confined, some IMP administrations and assessments could be completed by a HHN. Days 1, 2, 4, 7 could have a HHN visit for the PM dose. Days 5, 6, 8 could utilize a HHN for both doses. Day 3 will require an in-clinic visit for both doses. Day 9 visit will be in-clinic and no evening dose and, therefore, no HHN visit. Days 10-12 assessments will be done on site.
- ^e For Cohorts D and E, and any additional cohorts, all IMP administration may be QD or BID for each dosing day, as determined by the SRC.
- ^f Further detail regarding dose-modification and stopping criteria are described in [Section 4.2](#).
- ^g At Screening, a complete physical examination will be conducted including a neurological examination (gross motor and deep tendon reflexes), height and weight, and assessment of the following: general appearance, skin, head and neck, mouth, lymph nodes, thyroid, abdomen, musculoskeletal, cardiovascular,

neurological, and respiratory systems. At all other time points an abbreviated physical examination (pulmonary, cardiac, abdominal, and other systems related to any symptoms) will be conducted. Physical exams should be conducted prior to the morning dose on dosing days.

^h Vital signs will be taken at Screening, every day prior to the morning dose, and at the Follow-up visit. See detailed level of assessments for Day 3 and 9 in [Table 6](#) for additional times vital signs are taken. Vital signs include temperature, HR, and BP after resting for at least 5 minutes. On Day 2 and once on Day 9 (see [Table 6](#) for Day 9 instructions), vitals should include HR and BP taken in the supine position, one standing for 2 minutes, and one time standing for 5 minutes. All other HR and BP measurements should be the mean of 3 measurements taken in supine position, and BP should be taken via an automated recorder during confinement or during a clinic visit, and, if available, during home health nurse visits. On Day 1, patient will be ineligible to dose if HR ≥ 95 bpm at predose, if the average of 3 readings is higher than 95 bpm.

ⁱ Changes in a Baseline condition after the ICF is signed but before IMP is administered are recorded on the medical history eCRF unless the change is considered an AE related to a study procedure. All changes that occur after administration of the study medication are recorded as AEs.

^j Every effort should be made to maintain stable background HF treatment and to administer such treatments (including diuretic as applicable) at the same time every day throughout the duration of the study.

^k Two TTEs will be performed during screening, no fewer than 7 days apart. Eligibility must be confirmed by core laboratory for both TTEs. Effort should be made for the second TTE to be performed as close to time of dosing as is feasible, taking into account core laboratory processing time and patient availability. A full TTE should be performed at all time points indicated (with morning '0h' TTE on Day 3, Day 7 and Day 9 to be performed pre-dose). It is important that the TTEs are completed as close as possible to the scheduled time (± 1 hour). TTEs will be evaluated locally for changes that might affect stopping criteria and/or dose modification, but the official reading for final results will be done centrally by experts in a core laboratory in a blinded manner. For all patients, TTEs will be performed at the study site.

^l ECG telemetry will be initiated at least 1 hour prior to first dose (single-blind) on Day 1 and continued through Day 11 (ie, until about 48 hours post final double-blind dose on Day 9). Additional monitoring may be needed based on data and/or patient's tolerance to the treatment. Note: ECG telemetry is not required for patients who are not confined.

^m Continuous Holter monitoring will be acquired in 2 timepoints, first from Day 1 until Day 3 morning (before first dose of DB treatment, 48 hours total) and from Day 7 until Day 9. Holter may be set up any time on Day 7 and should be removed 48 hours later on Day 9. Holter may be set up by a trained home health nurse or at the study site. All patients, whether confined or not confined, must have Holter monitoring during the required times.

ⁿ Triplicate 12-lead ECG evaluations will be performed in the supine position after 10 minutes of rest at Screening and at Follow-up visit. See detailed schedule for Days 3 and 9. On Day 2, ECGs should be taken prior to the morning dose. On Day 4 ECG should be taken 7 hours post morning dose. On Day 7 (± 1 day) ECGs should be taken prior to morning dose. On Day 10, ECG is 24 hours post final dose and on Day 11 ECG is post 48 hours final dose. All predose ECGs should be taken within 2 hours of dose, and all other ECGs should be taken plus or minus 2 hours of time point indicated. The investigator may add extra 12-lead ECG safety assessments if there are any abnormal findings or if the investigator considers it required for any other safety reason. If the patient has any signs or symptoms suggestive of possible cardiac ischemia, additional ECGs should be obtained. These assessments should be recorded as unscheduled assessments. For all patients, ECGs will be performed at the study site.

^o ICD download to be performed unless site encounters significant technical difficulties and is required in case of shock(s) delivered by the ICD during the study.

^p Blood sample for HIV, HCV, and HBV will be collected at Screening.

^q Pregnancy tests, urine or blood based on the policy of the local institution or regulating Health Authority (eg, requirement for serum-based testing in the UK), should be performed on all females.

^r FSH tests will be included for potentially postmenopausal women.

- ^s Safety laboratory tests should be split and one sample evaluated by local lab and the other sent to Central Lab. Samples will be taken on days indicated prior to morning dose (except on Day 4, where labs will be taken at 7 hours post-dose). Day 2 local lab results must be evaluated prior to dosing on Day 3. If needed to accommodate local laboratory time tables, Day 2 samples may be taken on Day 1. Safety laboratory tests may be added at the discretion of the investigator. NOTE: Day 7 safety laboratory assessments can be performed ± 1 day if the assessments would fall on a weekend.
- ^t Troponin samples will be collected as indicated. The 0 hour assessment samples should be taken prior to dosing. On Day 10, samples should be taken 24 hours post last dose. On Day 11, samples should be taken 48 hours post last dose. Samples for troponin should be split, with one sample assayed locally in order to be locally reviewed by the investigator. Troponin I or Troponin T is acceptable for local troponin, based on availability of assay at site. The other sample will be analyzed at a Central Laboratory. Results of troponin from local lab should guide patient evaluation. Abnormal and/or rising troponin values (as per investigator judgment and taking into account potential Baseline troponin elevation) should lead to patient being clinically evaluated for possible myocardial ischemia. Also, if the patient has any signs or symptoms suggestive of possible cardiac ischemia, additional serial troponin (and other safety labs, including CK-MB samples) should be obtained. NOTE: Day 7 troponin samples can be taken ± 1 day if the assessments would fall on a weekend. Troponin testing performed at the Central Laboratory will be used for research purposes and will not be communicated to the study site except for Troponin I at Screening.

- ^w Refer to [Table 6](#) for Day 3 and Day 9 timepoints. On Day 10, samples should be taken 24 hours post final dose. On Day 11 samples should be taken 48 hours post final dose and Day 12 at 72 hours post final dose. It is important that PK sampling occurs as close as possible to the scheduled time. Unscheduled or additional PK samples may be collected if appropriate in the opinion of the investigator and/or Sponsor. For all patients, PK blood draws will be performed at the study site.

Table 6 Part 2 (MAD): Dosing Periods and Follow up – Detailed for Days 3 and 9

		Detailed Treatment and Observation for Randomized Study Drug on Days of First and Last Double-blind Dose (All-Day In Clinic Days 3 and 9)									
Hour	Predose ^a	Study Hour									
		0	1	2	3	4	5	6	7	9	12
Vital signs ^b	X								X		
12-lead ECGs ^c	X								X (Day 3 only)		
Troponin ^d	X								X (Day 3 only)		
PK (plasma) ^e	X		X	X	X	X	X	X	X	X	X
TTE ^g	X								X		

AE, adverse event; BP, blood pressure; CRF, case report form; ECG, electrocardiogram; HR, heart rate; ICD, implantable cardioverter defibrillator; IMP, investigational medicinal product; PK, pharmacokinetic; SAE, serious adverse event; SRC, Safety Review Committee; TTE, transthoracic echocardiography.

^a All predose assessments should be performed within 2 hours of administering the oral dose of MYK-491 or placebo, with the following exceptions: predose or trough PK blood samples should be taken within 1 hour predose, and ECG telemetry monitoring should be initiated at least 1 hour prior to the first dose.

^b Vital signs include temperature, HR, and BP after resting for at least 5 minutes. On Day 9, in the morning (predose), HR and BP should be taken once in the supine position, once after 2 minutes standing, once after 5 minutes standing. All other HR and BP measurements should be the mean of 3 measurements taken in supine position, and BP should be taken via an automated recorder.

^c Triplicate 12-lead ECG evaluations will be performed in the supine position after 10 minutes of rest at Screening, predose, and at 7 hours postdose. The predose ECG on Day 1 should be performed within 2 hours of dosing. The investigator may add extra 12-lead ECG safety assessments if there are any abnormal findings or if the investigator considers it required for any other safety reason. If the patient has any signs or symptoms suggestive of possible cardiac ischemia, additional ECGs should be obtained. These assessments should be recorded as unscheduled assessments. For all patients, ECGs will be performed at the study site.

[figure not shown]
^d Samples for troponin should be split with one sample assayed locally in order to be locally reviewed by the investigator. The other sample will be analyzed at a Central Laboratory. Results of troponin from local lab should guide patient evaluation. Abnormal and/or rising troponin values (as per investigator's judgment and taking into account potential Baseline troponin elevation) should lead to patient being clinically evaluated for possible myocardial ischemia.

[figure not shown]
Also, if the patient has any signs or symptoms suggestive of possible cardiac ischemia, additional serial troponin (and other safety labs, including CK-MB samples) should be obtained. Troponin testing performed at the Central Laboratory will be used for research purposes and will not be communicated to the study site except for Troponin I at Screening.

[figure not shown]
- c Plasma PK samples will be obtained at time points indicated. The 12-hour time point should be collected prior to evening dose on Day 3. It is important that PK sampling occurs as close as possible to the scheduled time. Unscheduled or additional PK samples may be collected if appropriate in the opinion of the investigator and/or Sponsor. For all patients, PK blood draws will be performed at the study site.

-
- g It is important that the TTEs are completed as close as possible to the scheduled time (± 1 hour). TTEs will be evaluated locally for changes that might affect dosing decision for others in the cohort, but the official reading will be done centrally by experts in a core laboratory in a blinded manner with results provided to the SRC. For all patients, TTEs will be performed at the study site.

-
-
-

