The bioanalyst assaying the PK samples will be unblinded so only the appropriate samples will be analyzed. On days in which the patients received placebo, only 1 sample obtained at about the time of the predicted maximum plasma concentration will be assayed to ensure that the patient received placebo.

7**STUDY TREATMENT**

IMP is defined as MYK-491 or placebo. In Part 1 (SAD), study patients will receive separate ascending doses of MYK-491 (2 to 3 doses) and a single dose of matching placebo.

In Part 2 (MAD), study patients will receive single-blind placebo BID for Days 1 and 2 and will then receive DB treatment (either placebo or MYK-491) for 7 days (Days 3 through 9). In Cohorts A, B, and C, on Day 9 patients will receive a single dose of placebo or MYK-491 in the morning for serial PK/PD assessments, while on Days 3 through 8 patients in these cohorts will receive placebo or MYK-491 BID.

In optional Cohorts D and E, and possible additional cohorts, patients may receive placebo or MYK-491 QD or BID dosing as determined by SRC.

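### Table 5: the Day 4 visit cells for non-confined ICD patients conflict with footnote d and with the rule that PK samples are drawn at the site, so the Day 4 predose sample can be missed

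*Combined protocol and SAP*

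**What the plan says.** Table 5 has two visit rows for patients who are not confined. In the row "Clinic visit mandatory ^c" the Day 4 entry is 7h alone. In the row "Clinic visit (optional) or HHN visit ^d" the Day 4 entry is AM and PM. The PK row asks for Day 4 samples at 0h and 7h.

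Three footnotes bear on these cells:

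- Footnote d, attached to the optional/nurse row, states: "Days 1, 2, 4, 7 could have a HHN visit for the PM dose. Days 5, 6, 8 could utilize a HHN for both doses".
- Footnote w, on PK, states: "For all patients, PK blood draws will be performed at the study site". Footnote b says the same of ECGs, TTEs and PK.
- Footnote a to Table 6, the detailed schedule for Days 3 and 9, sets the timing: "predose or trough PK blood samples should be taken within 1 hour predose".

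Section 4.1.2 lets ICD patients live near the unit if they can come back for all dosing and serial PK. As an alternative, it lets a home health nurse give study drug and do whatever can be done off site. Section 7 adds: "In optional Cohorts D and E, and possible additional cohorts, patients may receive placebo or MYK-491 QD or BID dosing".

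**The concern.** The grid is what a site coordinator works from. Read alone, it lets a nurse give the Day 4 morning dose at home and requires attendance only seven hours later. The 0h sample has to come before that dose and has to be drawn at the site, so the two instructions cannot both be met.

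What is at stake is one scheduled PK sample. It lies between the last Day 3 sample at 12 h (Table 6) and the Day 4 7h sample, which is 31 h after the first double-blind dose. Its value depends on the regimen. With twice-daily dosing it is a trough. With once-daily dosing it closes the first dosing interval. AUC over that interval is the Day 3 input to the accumulation ratio, a secondary endpoint (Sections 11.2.2 and 11.3.5). Any loss would follow ICD status and site practice, not chance.

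**Working it through.** No power or sample-size figure is involved. The first check is a comparison of the rows.

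**Optional/nurse row against footnote d, by study day**

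| Day | Mandatory clinic | Optional clinic or nurse | Nurse use under footnote d | Agree? |
|---|---|---|---|---|
| 1 | AM, 3PM | PM | PM | yes |
| 2 | AM, 7h | PM | PM | yes |
| 4 | 7h | AM, PM | PM | **no** |
| 5 | none | AM, PM | both doses | yes |
| 6 | none | AM, PM | both doses | yes |
| 7 | AM | PM | PM | yes |
| 8 | none | AM, PM | both doses | yes |

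Days 3 and 9 are full clinic days. Day 4 is the only mismatch. It looks like a slip: the other Day 4 site assessments with a stated time (TTE, 12-lead ECG, safety laboratory tests, troponin) are all at 7h, and PK is the only 0h item. In the extracted text the later PK cells sit one column late, but the Day 4 cell is fixed by its place directly after the Day 3 multiple-sample cell.

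**Clock, with the Day 3 morning dose at 0 h**

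- Last Day 3 sample: 12 h, before the evening dose in twice-daily cohorts.
- Day 4 0h sample: 24 h after the first dose. On 12-hourly dosing it is 24 − 12 = 12 h after the second dose.
- Day 4 7h attendance: 24 + 7 = 31 h, after the morning dose, so it cannot replace a predose sample.

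**Twice-daily cohorts (A to C).** The accumulation ratio uses Cmax and AUC over the dosing interval on Days 3 and 9. For a 12 h interval the Day 3 input is the 0–12 h profile, collected entirely in clinic. Without the Day 4 0h sample, one trough is lost and that input is intact.

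**Once-daily cohorts, if this schedule were kept.** The interval is 24 h. On Day 9 its end is secured by the mandatory Day 10 morning visit. On Day 3 its end is the Day 4 0h sample. Without it, 12–24 h must be extrapolated.

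The size of that segment needs kinetics that the available text does not give, so the following are assumptions: a one-compartment oral profile, half-life 8 to 24 h, Tmax 3 to 7 h.

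- ke = ln 2 / half-life; ka solves Tmax = ln(ka/ke) / (ka − ke).
- Up to a constant, AUC(0–T) = (1 − e^(−ke·T))/ke − (1 − e^(−ka·T))/ka.
- Share = [AUC(0–24) − AUC(0–12)] / AUC(0–24).

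Half-life 8 h, Tmax 3 h: ke = 0.0866, ka = 0.846; AUC(0–12) = 6.280, AUC(0–24) = 8.917; share = 2.638/8.917 = 0.296.

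Half-life 24 h, Tmax 7 h: ke = 0.0289, ka = 0.407; AUC(0–12) = 7.701, AUC(0–24) = 14.854; share = 7.153/14.854 = 0.482.

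A cohort of 8 randomized 3:1 has 6 active patients, so each active patient affected is 1/6, about 17%, of a dose group.

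**The case against.** The strongest reply is that the plan, read as a whole, already brings the patient in. The Day 4 cell offers an optional clinic visit as well as a nurse, footnote d rules out the nurse for that morning dose, and footnotes b and w keep PK at the site. This stands against a tempting stronger reading, that these patients have no visit at which the sample could be taken. They have one; it is just not mandatory. The reply does not remove the conflict, because the cell still permits what its own footnote excludes. The Section 4.1.2 condition about returning for serial PK does not settle it either, since the nurse route follows as an alternative.

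A reader might also infer that every non-confined ICD patient is affected. Footnote b says otherwise: those staying nearby must come back for all dosing and assessments. Only patients whose site uses a nurse for the Day 4 morning dose are exposed.

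Nor do the documents support a claim that first-dose PK is compromised in Cohorts A to C. An evening dose is given on Day 3, the 12 h sample before it is taken in clinic, and the accumulation ratio does not need the Day 4 sample.

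The once-daily consequence is conditional. Table 5 is headed for twice-daily treatment, once-daily cohorts are optional, and Section 9 applies the Appendix 2 timelines to Cohort A, after which the Safety Review Committee may change them. That limits the consequence but does not remove it, because footnote e to Table 5 carries the grid over to cohorts that may be once daily.

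Finally, the one-hour predose window is stated under Table 6 and not for Day 4. The point does not depend on it: a visit seven hours after the dose is too late under any window.

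**Conclusion.** The inconsistency is real and confined to Day 4. Following the grid as printed, with a nurse giving the Day 4 morning dose, loses a scheduled PK sample; following footnote d, or using the optional morning clinic visit, keeps it. The number exposed is the home-nurse subset of non-confined ICD patients, which the documents do not give.

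In twice-daily cohorts the effect is small. In an optional once-daily cohort on this schedule, Day 3 AUC0-24 in affected patients would be part observed and part extrapolated, while Day 9 was sampled to 24 h. The 30% to 48% is the part of AUC beyond 12 h under assumed kinetics. It should not be read as bias in the accumulation ratio: extrapolating from the 7, 9 and 12 h samples does not lose that share, and no error in the ratio has been calculated. The correction is worth making because it is cheap and protects a scheduled sample.

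**What to change.** Reconcile the Day 4 visit cells in Table 5 with footnote d and the PK row. Change the Day 4 mandatory clinic entry from 7h to AM and 7h, and leave only PM in the Day 4 optional/nurse cell. The grid then agrees with footnote d on every day it lists, and the 0h draw falls at a required site visit. No dose or regimen changes.

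The cost is a two-cell table correction and one extra morning attendance, for patients who would otherwise be dosed at home that morning, on a day when they already attend at 7h.
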